3.1.1.4. Onset Day of Each Local Reaction

The onset day of each local reaction will be derived. Onset day is defined as the first day of reporting any severity.

For the onset day of each local reaction, if a subject reports changes in severity of the local reaction, only the first day of reporting that specific local reaction will be counted.

3.1.1.5. Presence of Severe Local Reaction on Each Day

Presence (yes or no) of any severe local reaction on each of the 14 days (Day 1 through Day 14) follows the derivation as described in Table 5.

Table 5. Derived Variables for Any Severe Local Reaction on Each Day

Variable	Yes (1)	No (0)	Missing (.)
Any severe local reaction on a specific day	Subject reports the severe reaction as “yes” on a specific day for any of the 3 local reactions.	Subject reports the reaction as a combination of any of the following: “no,” “mild,” “moderate,” or missing on that specific day.	Subject reports all 3 local reactions as “missing” on that specific day.

3.1.2. Systemic Events

Systemic events, including fever, fatigue, headache, vomiting, nausea, diarrhea, muscle pain, and joint pain, are reported via e-diary from Day 1 through Day 14 after each vaccination, where Day 1 is the day of vaccination. The derivations below for systemic events will be handled similarly to the way local reactions are handled for presence, severity level, duration, onset day, and severe systemic events on each day.

1. Presence (yes or no) of each systemic event on any day (Day 1 through Day 14).
2. Presence (yes or no) of any systemic event on any day (Day 1 through Day 14).
3. Maximum severity of each systemic event on any day (Day 1 through Day 14).
4. Maximum severity of any systemic event on any day (Day 1 through Day 14).
5. Duration of each systemic event.
6. Onset day of each systemic event.
7. Presence (yes or no) of any severe local reaction on each of the 14 days.

The systemic events gradings are provided in Table 6.

Table 6. Grading Scale for Systemic Events

	Mild Grade 1	Moderate Grade 2	Severe Grade 3	Grade 4^a
Fatigue (= tiredness in diaries)	Does not interfere with activity	Some interference with activity	Prevents daily routine activity	Emergency room visit or hospitalization for severe fatigue
Headache	Does not interfere with activity	Some interference with activity	Prevents daily routine activity	Emergency room visit or hospitalization for severe headache
Vomiting	1 to 2 times in 24 hours	>2 times in 24 hours	Requires intravenous hydration	Emergency room visit or hospitalization for severe vomiting
Nausea	Does not interfere with activity	Some interference with activity	Prevents daily routine activity	Emergency room visit or hospitalization for severe nausea
Diarrhea	2 to 3 loose stools in 24 hours	4 to 5 loose stools in 24 hours	6 or more loose stools in 24 hours	Emergency room visit or hospitalization for severe diarrhea

Table 6. Grading Scale for Systemic Events

	Mild Grade 1	Moderate Grade 2	Severe Grade 3	Grade 4^a
Muscle pain	Does not interfere with activity	Some interference with activity	Prevents daily routine activity	Emergency room visit or hospitalization for severe muscle pain
Joint pain	Does not interfere with activity	Some interference with activity	Prevents daily routine activity	Emergency room visit or hospitalization for severe joint pain

- a. Grade 4 assessment should be made by the investigator using the AE severity grading scale. The assessment will be collected on the AE case report form and thus not reported from the e-diary.

Fever is defined as an oral temperature of $\geq 100.4^{\circ}\text{F}$ ($\geq 38.0^{\circ}\text{C}$). The highest temperature for each day will be recorded in the e-diary. Any temperature recorded as $< 95.0^{\circ}\text{F}$ (35.0°C) or $> 107.6^{\circ}\text{F}$ (42.0°C) will be treated as a data entry error and excluded from the analyses. For reporting purposes, fever will be analyzed using the following temperature ranges:

- 38.0°C to 38.4°C (100.4°F – 101.1°F)
- 38.5°C to 38.9°C (101.2°F – 102.0°F)
- 39.0°C to 40.0°C (102.1°F – 104.0°F)
- $> 40.0^{\circ}\text{C}$ ($> 104.0^{\circ}\text{C}$)

3.1.3. Use of Antipyretic/Pain Medication

Antipyretic/pain medications used to treat symptoms are recorded in the e-diary. This variable will be presented along with systemic events summary, but not counted as a systemic event. The following variables will be derived:

1. Use of antipyretic/pain medication on “any day (Days 1-14)” after vaccination.
2. Duration of use of antipyretic/pain medication after vaccination.
3. Onset day of antipyretic/pain medication use after vaccination.

3.1.4. Adverse Events

AE reporting will be based on the specific reporting period. Standard algorithms for handling missing AE dates and missing AE severity will be applied as described in the Pfizer Vaccine data standard rules.

As this is a Phase 1/2 study, with limited sample size included in each vaccine group, the value of applying the 3-tier approach is limited. Therefore, because of a small number of

subjects in each dose/formulation group, safety assessment may be best carried out using descriptive statistics.

For AEs within 1 month after each vaccination, the interval calculation will be based on the study visit. For example, for the Primary Study Cohort - Stage 1, AEs within 1 month after Vaccination 1 will include any AE that occurred from the day of Vaccination 1 until the day before the 1-month post-Vaccination 1 visit (Visit 2). In general, this will be derived for each vaccination:

- Primary Study Cohort - Stage 1: AEs within 1 month after Vaccination 1.
- Primary Study Cohort - Stage 2: AEs within 1 month after Vaccination 2.
- RSV Vaccine Month-0, Month-2 Cohort – AEs within 1 month after Vaccination 1.
- RSV Vaccine Month-0, Month-2 Cohort – AEs within 1 month after Vaccination 2.

The following derivations/summaries will be included for each of the above:

1. Proportions of subjects reporting AEs during this interval summarized for each system organ class (SOC) and preferred term (PT) (and “any event”), separately.
2. Proportion of subjects reporting any AE during this interval.
3. Proportion of subjects reporting any MAE during this interval.
4. Proportion of subjects reporting any SAE during this interval.
5. Proportion of subjects reporting any related AE during this interval.
6. Proportion of subjects reporting any severe AE during this interval.
7. Proportion of subjects reporting any intermediate AE. Intermediate AE is defined as an AE reported within the first 30 minutes after vaccination.
8. Proportion of subjects reporting any AE leading to withdrawal during this interval.
9. Proportion of subjects reported any AE of specific interest (Refer to Section 8.4.2 of the protocol for details on the diseases/disorders included in this category).

3.1.5. Medically Attended AEs and Serious AEs

Proportions of subjects reporting SAEs and MAEs will be summarized for each SOC and PT (and “any event”), separately, for the following intervals:

- Primary Study Cohort - Stage 1: MAEs (or SAEs) through 12 months after Vaccination 1.

CCI

PFIZER CONFIDENTIAL

- Primary Study Cohort - Stage 2: MAEs (or SAEs) through 12 months after Vaccination 2.
- RSV Vaccine Month-0, Month-2 Cohort: MAEs (or SAEs) through 12 months after Vaccination 2.

3.2. Secondary Endpoint(s)

Primary Study Cohort - Stage 1:

- RSV A– and RSV B–neutralizing antibody titers measured before and 1 month after Vaccination 1.
- Hemagglutination inhibition assay (HAI) titers for all strains in the SIIV measured before and 1 month after Vaccination 1.

3.2.1. RSV A– and RSV B–Neutralizing Antibody Titers

RSV A– and RSV B– neutralizing antibody titers will be determined on all sera collected at applicable visits for antibody testing.

Titers above the lower limit of quantitation (LLOQ) are considered accurate and their quantitated values will be reported. Refer to [Section 5.3.2](#) for LLOQs. Titers below the corresponding LLOQ or denoted as below the limit of quantitation (BLQ) will be set to $0.5 \times \text{LLOQ}$ for analysis. Missing assay results will not be imputed. Calculations and derivations will be based on imputed values.

In addition to titer, the neutralizing titer (NT) fold rise from before vaccination will be derived for both RSV A and RSV B as detailed below:

1. For the Primary Stage Cohort - Stage 1: NT fold rise will be derived from before Vaccination 1 to each post–Vaccination 1 visit with NT assay performed.
2. For the Primary Stage Cohort - Stage 2:
 - a. NT fold rise will be derived from before Vaccination 2 to each post–Vaccination 2 visit with NT assay performed.
 - b. NT fold rise will be derived from before Vaccination 1 to each post–Vaccination 1 visit (including any post–Vaccination 2 visits and at the Vaccination 2 visit) with NT assay performed.
 - c. NT fold rise will be derived from 1 month after Vaccination 1 to 1 month after Vaccination 2.

3. For the RSV Vaccine Month-0, Month-2 Cohort:
 - a. NT fold rise will be derived from before Vaccination 1 to each applicable post-Vaccination 1 visit (note: 2 months after Vaccination 1 is the same as before Vaccination 2).
 - b. NT fold rise will be derived from before Vaccination 2 to each post-Vaccination 2 visit with NT assay performed.
 - c. NT fold rise will be derived from 1 month after Vaccination 1 to 1 month after Vaccination 2.

For calculating a fold rise, $< \text{LLOQ}$ will be converted to $0.5 \times \text{LLOQ}$ for a numerator, and $< \text{LLOQ}$ will be converted to LLOQ for a denominator when only one of either the numerator or denominator is $< \text{LLOQ}$. If both the numerator and denominator are $< \text{LLOQ}$, then both will be converted in the same way.

3.2.2. HAI Titers

Hemagglutination inhibition antibody titers will be measured by the standard HAI for the 3 influenza vaccine strains contained in the SIIV. The assay will be performed by VisMederi (Siena, Italy), with $\text{LLOQ} = 1:10$ for each strain.

Titers above the LLOQ are considered accurate and their quantitated values will be reported. Titers below the corresponding LLOQ or denoted as BLQ will be set to $0.5 \times \text{LLOQ}$ for analysis. Missing assay results will not be imputed. Calculations and derivations will be based on imputed values.

For the Primary Stage Cohort - Stage 1: HAI fold rise will be derived from before Vaccination 1 to 1 month after Vaccination 1 for each strain tested.

For the Primary Stage Cohort - Stage 2: HAI fold rise will be derived from before Vaccination 2 to 1 month after Vaccination 2 for each strain tested.

In addition to the HAI titer and HAI fold rise, 2 binary variables will be derived for each of the influenza strains tested for both cohorts:

1. HAI seroprotection before and after SIIV vaccination: HAI titer is $\geq 1:40$.
2. HAI seroconversion after SIIV vaccination:
 - a. If the HAI titer is $< 1:10$ (LLOQ for HAI) before SIIV administration, seroconversion is achieved if the postvaccination titer is $\geq 1:40$.
 - b. If the HAI titer is $\geq 1:10$ before SIIV administration, seroconversion is achieved if the fold rise from before SIIV to the postvaccination titer is ≥ 4 .

3.3. Exploratory Endpoints

Primary Study Cohort - Stage 1:

- RSV A– and RSV B–neutralizing antibody titers measured at 1 week (PBMC subjects) and 3, 6, and 12 months after Vaccination 1.
- Plasmablast frequencies and T-cell phenotype and functional analysis before and 1 week after Vaccination 1 (PBMC subjects).
- Memory B-cell and T-cell frequencies and their functional analysis before vaccination and 1 and 6 months after Vaccination 1.
- Immunoglobulin G (IgG) titers against prefusion F (preF) before vaccination and 1, 3, 6, and 12 months after Vaccination 1.
- IgG titers to nonvaccine RSV antigens before vaccination and 1, 3, 6, and 12 months after Vaccination 1.
- H3N2-neutralizing antibody titers measured before vaccination and 1 month after Vaccination 1.

Primary Study Cohort - Stage 2:

- Local reactions within 14 days after Vaccination 2.
- Systemic events within 14 days after Vaccination 2.
- AEs within 1 month after Vaccination 2.
- MAEs and SAEs through 12 months after Vaccination 2.
- RSV A– and RSV B–neutralizing antibody titers measured at 1 week (PBMC subjects) and 1, 3, 6, and 12 months after Vaccination 2.
- Plasmablast frequencies and T-cell phenotype and functional analysis before Vaccination 2 and 1 week after Vaccination 2 (PBMC subjects).
- Memory B-cell and T-cell frequencies and their functional analysis before Vaccination 2 and 1 and 6 months after Vaccination 2.
- IgG titers against preF before Vaccination 2 and 1, 3, 6, and 12 months after Vaccination 2.
- IgG titers to nonvaccine RSV antigens before Vaccination 2 and 1, 3, 6, and 12 months after Vaccination 2.

- HAI titers for all strains in the SIIV measured before and 1 month after Vaccination 2.
- H3N2-neutralizing antibody titers measured before Vaccination 2 and 1 month after Vaccination 2.

RSV Vaccine Month-0, Month-2 Cohort

- Local reactions within 14 days after Vaccinations 1 and 2.
- Systemic events within 14 days after Vaccinations 1 and 2.
- AEs within 1 month after Vaccinations 1 and 2.
- AEs from Vaccination 1 through 1 month after Vaccination 2.
- MAEs and SAEs through 12 months after Vaccination 2.
- RSV A- and RSV B-neutralizing antibody titers measured at scheduled time points before and after each vaccination scheduled.
- Plasmablast frequencies and T-cell phenotype and functional analysis before each vaccination and 1 week after Vaccinations 1 and 2 (PBMC subjects).
- Memory B-cell and T-cell frequencies and their functional analysis before each vaccination and 1 and 6 months after Vaccinations 1 and 2.
- IgG titers against preF at scheduled time points before and after each vaccination.
- IgG titers to nonvaccine RSV antigens at scheduled time points before and after each vaccination.

3.3.1. H3N2-Neutralizing Titers

H3N2-neutralizing antibody titers will be performed by VisMederi (Siena, Italy). The LLOQ for this assay is 1:10.

Titers above the LLOQ are considered accurate and their quantitated values will be reported. Titers below the corresponding LLOQ or denoted as BLQ will be set to $0.5 \times \text{LLOQ}$ for analysis. Missing assay results will not be imputed. Calculations and derivations will be based on imputed values.

For the Primary Stage Cohort - Stage 1: H3N2 NT fold rise will be derived from before Vaccination 1 to 1 month after Vaccination 1.

For the Primary Stage Cohort - Stage 2: H3N2 NT fold rise will be derived from before Vaccination 2 to 1 month after Vaccination 2.

CCI

PFIZER CONFIDENTIAL

In addition to the H3N2 NT and fold rise, 2 binary variables will be derived:

1. Seroprotection for H3N2 NTs is defined as follows: H3N2 NT is $\geq 1:80$.
2. Seroconversion for H3N2 NTs after vaccination is defined based on the NT before SIV vaccination:
 - When the NT is $< 1:20$ before SIV, seroconversion is achieved if the postvaccination NT is $\geq 1:80$.
 - When the NT is $\geq 1:20$ after SIV, seroconversion is achieved if the fold rise from the prevaccination to the postvaccination NT is ≥ 4 .

Rationale:

Although no widely agreed cutoff protective level for NTs is available, estimates in the literature for neutralizing protective levels against H3N2 viruses range from 1:40 to 1:160. However, maximal protection against H3N2 was achieved at an HAI titer of 1:160 and an NT of 1:320, about twice as high a protective titer for H3N2 with neutralization assay as with HAI. Considering LLOQ is the same for HAI and neutralization assay, we chose 1:80 to define seroprotection, which is consistent with existing literature.^{1,2}

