5.3.2. Immunogenicity Data

Any assay results above LLOQ are considered accurate and their quantitated values will be reported. Assay results noted as the upper limit of quantitation (ULOQ) will be set to the value of ULOQ for analysis. Values below the LLOQ or denoted as BLQ, or limit of detection (LOD), will be set to $0.5 \times \text{LLOQ}$ for analysis. For calculating a fold rise, $< \text{LLOQ}$ will be converted to $0.5 \times \text{LLOQ}$ for a numerator, and $< \text{LLOQ}$ will be converted to LLOQ for a denominator when only one of either the numerator or denominator is $< \text{LLOQ}$. If both the numerator and denominator are $< \text{LLOQ}$, then both will be converted in the same way.

CCI

CCI

CCI

PFIZER CONFIDENTIAL

Page 29

CCI

CCI

Values for sera that are insufficient (QNS), indeterminate results, or values recorded as “not done” will be set to “missing.” Additionally, any time point with no blood draws will not be included in the analysis. No imputation will be done for these missing values.

CCI

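### The second branch of the H3N2 seroconversion rule tests the titer after SIIV, contradicting its own lead-in; coded as written without precedence, the 1:80 requirement for low-baseline subjects has no effect

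*SAP*

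**What the plan says.** SAP 3.3.1 introduces the rule with "Seroconversion for H3N2 NTs after vaccination is defined based on the NT before SIV vaccination" (the section writes SIV where the rest of the SAP mostly writes SIIV). Two branches follow.

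- Branch 1: an NT below 1:20 "before SIV, seroconversion is achieved if the postvaccination NT is" at least 1:80.
- Branch 2: an NT of at least 1:20 "after SIV, seroconversion is achieved if the fold rise from the prevaccination to the postvaccination NT is" at least 4.

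The parallel HAI rule in SAP 3.2.2 splits on the prevaccination titer in both branches. Its second branch covers a titer of at least 1:10 "before SIIV administration, seroconversion is achieved if the fold rise from before SIIV to the postvaccination titer is" at least 4.

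Two other provisions bear on the fold rise. SAP 3.3.1 states "The LLOQ for this assay is 1:10", sets lower results to half that value, and adds "Calculations and derivations will be based on imputed values". SAP 5.3.2 has a separate convention for fold rises: a result below the LLOQ "will be converted to LLOQ for a denominator when only one of either the numerator or denominator is" below the LLOQ.

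SAP 6.3.5 repeats for H3N2 the analyses that SAP 6.2.2 sets out for HAI. These include seroconversion rates with 95% CIs by vaccine group.

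**The concern.** The two branches should divide subjects by baseline titer. As written, branch 1 tests the titer before SIIV and branch 2 the titer after it, so they overlap. A subject with a pre titer of 1:10 and a post titer of 1:40 fails branch 1, but also meets the condition of branch 2 and passes it on a 4-fold rise. The SAP does not say which branch wins.

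The prespecified definition therefore allows two competent programmers to report different seroconversion rates from the same data. On one of the two readings, the 1:80 threshold, which SAP 3.3.1 justifies at some length as the seroprotection level, has no role in seroconversion.

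**Working it through.** The documents state no rate for this endpoint, so there is no figure to reproduce. The check compares the possible readings of the rule.

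**Inputs.** LLOQ 1:10; branch 1 split at 1:20 and criterion 1:80; branch 2 split at 1:20 and criterion 4-fold (all SAP 3.3.1). The denominator for a pre titer below the LLOQ is 5 (0.5 × 10, SAP 3.3.1) or 10 (SAP 5.3.2).

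**Readings, with titers as reciprocals.**

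- Literal, no precedence: (pre < 20 and post ≥ 80) or (post ≥ 20 and fold ≥ 4).
- Corrected: if pre < 20, post ≥ 80; if pre ≥ 20, fold ≥ 4.
- Literal text with branch 1 first: if pre < 20, post ≥ 80; otherwise post ≥ 20 and fold ≥ 4.

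**Reduction.**

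1. If pre < 20 and post ≥ 80, the fold rise exceeds 80/20 = 4 and post is at least 20. Everyone who passes branch 1 therefore also passes branch 2.
2. The smallest denominator is 5, so a fold rise of at least 4 implies post ≥ 4 × 5 = 20. The condition post ≥ 20 removes nobody.
3. The literal reading is therefore fold ≥ 4 and nothing else.
4. In the corrected rule, pre ≥ 20 with fold ≥ 4 implies post ≥ 80. The corrected rule is therefore fold ≥ 4 and post ≥ 80.
5. The two readings differ exactly for fold ≥ 4 with post < 80, which requires pre < 20. No subject moves the other way.
6. With branch 1 first, the remaining subjects have pre ≥ 20, and fold ≥ 4 already gives post ≥ 80. The result equals the corrected rule.

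**Pairs affected on a 2-fold dilution grid (below 10, then 10 to 1280).**

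| Pre | Post | Fold rise, 5.3.2 rule | Fold rise, 3.3.1 imputation | Literal | Corrected |
|---|---|---|---|---|---|
| <10 | 40 | 40/10 = 4 | 40/5 = 8 | yes | no |
| 10 | 40 | 40/10 = 4 | 40/10 = 4 | yes | no |
| <10 | 20 | 20/10 = 2 | 20/5 = 4 | only with 3.3.1 | no |

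Enumerating the full grid gave no other differences, and none with branch 1 first. Low-baseline subjects with pre 10 and post 20, or any post titer of 10 or below, are non-converters on every reading. Subjects with pre ≥ 20 and post < 20 fall in neither branch, which is harmless because their titer fell.

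**Size under assumptions.** Since the documents give no H3N2 titer distribution, I assumed a log-normal baseline (log2 SD 2) and a log-normal rise (log2 SD 1.5), with titers rounded down to the 2-fold grid and 1,000,000 draws per scenario. The excess is the literal rate minus the corrected rate, in percentage points, for geometric mean fold rises of 2, 4 and 8.

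| Baseline GMT | Share with pre < 20 | Excess, 5.3.2 rule (2 / 4 / 8) | Excess, 3.3.1 imputation (2 / 4 / 8) |
|---|---|---|---|
| 10 | 0.69 | 6.9 / 11.1 / 13.3 | 13.1 / 20.5 / 23.8 |
| 20 | 0.50 | 6.2 / 9.4 / 10.4 | 10.6 / 15.8 / 17.0 |
| 40 | 0.31 | 4.4 / 6.4 / 6.6 | 7.0 / 9.9 / 10.0 |
| 80 | 0.16 | 2.6 / 3.5 / 3.4 | 3.8 / 5.1 / 4.8 |
| 160 | 0.07 | 1.2 / 1.6 / 1.4 | 1.6 / 2.1 / 1.9 |

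For example, at GMT 20 with a 4-fold mean rise and the 5.3.2 rule, the literal rate is 50.7% and the corrected rate 41.3%, a difference of 9.4 points. In a group of about 31 (Protocol Table 4), one misclassified subject moves the rate by 1/31 = 3.2 points.

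**The case against.** The strongest reply is that the lead-in governs. It makes the baseline titer the basis of the rule. A programmer who follows it, or who simply codes branch 1 first and branch 2 as the alternative, obtains the corrected result for every subject. On that view the word is a slip with no numerical consequence. The programming rules, which SAP section 2 says are prepared separately, may already handle it. This stands as far as it goes: a reader might infer that the reported rate will be inflated, and the documents do not establish that. What remains is that the branch contradicts its lead-in and the SAP states no precedence.

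A reader might also infer that every low-baseline subject who misses 1:80 would be counted. That is not so: only those with at least a 4-fold rise are, which on a 2-fold grid means a post titer of 1:40, or also 1:20 from below the LLOQ with the 3.3.1 imputation.

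Finally, a reader might infer that the assessment of RSV vaccine interference with SIIV is biased. SAP 6.2.2.2 makes that assessment with ratios of GMTs, which do not use this rule. Seroconversion is summarized by group, and SAP 5.2.1 says only that CIs for differences in proportions may be computed for some exploratory analyses. The Protocol 9.2.2 seroconversion definition is for HAI, and the protocol has no H3N2 rule. Unequal inflation between arms through chance baseline imbalance is conceivable, but nothing in the documents allows it to be sized.

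**Conclusion.** The contradiction is certain and the intended reading is clear. The lead-in, branch 1 and the HAI rule all use the prevaccination titer, and the corrected H3N2 thresholds (1:20 and 1:80) are twice the HAI ones (1:10 and 1:40).

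The numerical consequence is conditional. It is zero if branch 1 takes precedence. If the branches are coded without precedence, the rate can only rise. Under the assumed distributions and the 5.3.2 fold-rise rule, the excess is about 1 to 2 points at a baseline GMT of 160 and about 7 to 13 at a GMT of 10. With the 3.3.1 imputation it reaches about 24 points at a GMT of 10. These figures illustrate and do not bound the effect; other spreads or baselines would change them.

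The effect is confined to exploratory, descriptive H3N2 seroconversion rates. The primary safety endpoints, the secondary HAI endpoint and the GMR comparisons are untouched. The point is worth correcting because a prespecified endpoint rule is wrong as written.

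**What to change.** In the second branch of SAP 3.3.1, replace the word after with before, so that the branch covers subjects whose NT is at least 1:20 before SIIV and requires a fold rise of at least 4.

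The branches are then mutually exclusive and cover everyone with both titers. The choice between the 3.3.1 and 5.3.2 denominators also stops mattering for seroconversion, because no subject in the second branch has a pre titer below the LLOQ. That choice still affects the H3N2 GMFR, so it would help to state in 3.3.1 which convention applies.

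The cost is one word in the SAP and a check that the derivation program matches. No design, sample size or data collection changes.
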